## LIST OF ABBREVIATIONS

AE	Adverse Event/Adverse Experience
ANOVA	Analysis of Variance
BIS/BAS	Behavioral Inhibition System / Behavioral Approach System
CFR	Code of Federal Regulations
Co-I	Co-Investigator
CRF	Case Report Form
DHHS	Department of Health and Human Services
DMV	Department of Motor Vehicles
EEG	Electroencephalogram
EMG	Electromyography
FDA	Food and Drug Administration
GCP	Good Clinical Practice
Hz	Hertz
ICF	Informed Consent Form
ICH	International Conference on Harmonization
IDE	Investigational Device Exemption
ITCP	Inter-trial phase coherence
LAR	Legally Authorized Representative
MRI	Magnetic Resonance Imaging
NAMI	National Alliance on Mental Illness
NIH	National Institutes of Health
NIMH	National Institute of Mental Health
OHRE	Office of Human Research Ethics
OHRP	Office for Human Research Protections
PHI	Protected Health Information
PI	Principal Investigator
SAE	Serious Adverse Event/Serious Adverse Experience
SMC	Safety Monitoring Committee
SPI	Serial Peripheral Interface
SOP	Standard Operating Procedure
TMS	Transcranial Magnetic Stimulation
UE	Unexpected Event
UNC	University of North Carolina
UNC-CH	University of North Carolina at Chapel Hill
US	United States
WM	Working memory
WPLI	Weighted Phase Lag Index

STUDY SUMMARY

Title	Causal role of theta and alpha oscillations in output-gating
Short Title	STAR
Protocol Number	21-0248
Phase	Pilot
Methodology	Two phases, five-session, parallel arms design, active control
Study Duration	This study is expected to last for three years.
Study Center(s)	This is a two-phase, five-session, single-site study performed at the University of North Carolina at Chapel Hill.
Objectives (Purpose)	The purpose of this pilot study is to investigate the dynamics between theta and alpha oscillations in the control of working memory.
Number of Participants	200
Diagnosis and Main Inclusion Criteria	Eligible participants will be healthy adults between the ages of 18-35 with no history of mental or psychiatric disorder.
Description of Intervention (Procedures/methods)	The participants will perform a cognitive control task. During the task, rhythmic trains of transcranial magnetic stimulation will be delivered to the prefrontal cortex or parietal cortex. Participants will be screened for their ability to perform the task. Magnetic resonance imaging will be used to source localize regions of interest to be targeted. Electroencephalography will be collected concurrent with stimulation.
Related IRB Applications	18-1789

### 1.4 FUNDING SOURCES

Please list below the funding sources for this project:

Sponsor Name	UNC Ramses Number	Sponsor Type	Prime Sponsor Name	Prime Sponsor Type	Sponsor/Grant Number
NIMH	TBD	R01	TBD	TBD	TBD

**External Funding:** This project is externally funded through the National Institute of Mental Health (NIMH).

**UNC-CH Funding:** This project is not funded through UNC-CH.

**Classified:** This project is not classified.

### 1.5 SUMMARY OF CHANGES

Summary of changes to protocol:

CONFIDENTIAL

Version	Date	Reason
2.0	Oct 6 th , 2020	Expanded description of the primary and secondary outcomes. Expanded description of the statistical analysis plan. Inclusion of experimental flow figure.
3.0	Jan 29 th , 2021	IRB number included to reflect submission.
4.0	March 26 th , 2021	Clarification that there are not separate subject IDs for randomization, but that custom scripts handle randomization.
5.0	April 23 rd , 2021	Risk of physical injury from MRI and risk of hearing loss from TMS was added to Section 8. [name] was included as a medical monitor. Her description was added throughout, for example in Section 9.2 on Safety Oversight. An incidental findings of MRI protocol was added to Section 8.3.
6.0	May 27 th , 2022	Section 5.2 was updated to clarify that MRI is acquired during performance of the working memory task, which is stated elsewhere in the protocol.
7.0	Sept 21, 2025	Randomization was revealed to be parallel arms instead of crossover design. The protocol was updated accordingly to reflect this.

## 2 INTRODUCTION

This document is a protocol for a human research study. This study is to be conducted according to U.S. and international standards of Good Clinical Practice (FDA Title 21 Part 312 and International Conference on Harmonization guidelines), applicable government regulations and Institutional research policies and procedures.

### 2.1 BACKGROUND

The foundation of cognitive control is the ability of the brain to dynamically allocate limited resources to process input from the environment and manipulate internal representations as a function of behavioral demands (Miller and Cohen 2001, Gazzaley and Nobre 2012). The selective admittance of information from the environment is referred to as “input-gating” (Jensen and Mazaheri 2010). For example, the Posner task guides input-gating by presenting a cue at the start of each trial (pre-cue) that guides attention towards the likely location of a future stimuli (Posner 1980). In contrast, “output-gating” refers to the internal manipulation of previously acquired information, often manifested as prioritization, integration, sequencing, and transformation (Chatham, Frank et al. 2014, Chatham and Badre 2015, Wallis, Stokes et al. 2015). For example, the retrospective-cue working memory working memory task drives output-gating by presenting a cue in the delay period (retro-cue) that indicates in which hemifield items are more likely to be tested (Wallis, Stokes et al. 2015, Souza and Oberauer 2016). Output-gating comprises two intertwined cognitive processes: the *selection of relevant information* and the *suppression of irrelevant information*. These two cognitive processes have been correlated with functional interactions mediated by oscillatory activity in cortical networks in two distinct frequency bands: theta oscillations (4-7 Hz) in selection (Wallis, Stokes et al. 2015, Albouy, Weiss et al. 2017) and alpha oscillations (8-12 Hz) in suppression (Wallis, Stokes et al. 2015, Schneider, Mertes et al. 2016, Poch, Capilla et al. 2017, de Vries, van Driel et al. 2018, Poch, Valdivia et al. 2018).

Theta oscillations are generated in prefrontal cortex during the maintenance of internal representation in working memory (Jensen and Tesche 2002), and the magnitude of theta activity is further increased when internal representations are manipulated, a form of output-gating (Albouy, Weiss et al. 2017, Berger, Griesmayr et al. 2019). Low-frequency neural oscillations in prefrontal cortex are theorized to serve as top-down control signals as they couple to faster frequency activity in posterior cortex (Voytek, Kayser et al. 2015, Helfrich, Huang et al. 2017, Berger, Griesmayr et al. 2019) (see (Helfrich and Knight 2016) for a review). Recent experiments have found that brain stimulation to increase frontal theta activity or theta-frequency connectivity between prefrontal cortex and posterior cortex can improve cognitive performance (Polanía, Nitsche et al. 2012, Alekseichuk, Turi et al. 2016, Berger, Griesmayr et al. 2019, Reinhart and Nguyen 2019). Impaired cognition, especially in executive functions such as working memory, is prevalent in many psychiatric illnesses, including depression (Rose and Ebmeier 2006) and psychotic disorders (Gold, Barch et al. 2018). For example, people with major depressive disorder show decreased theta oscillations during task performance (Kane, Cavanagh et al. 2019). Thus, examining the causal role of theta oscillations in cognitive control will advance not only cognitive neuroscience but also provide a foundation for future investigations into how pathological changes of these oscillations may mediate impairment of cognition.

A complementary process to the selection of relevant information is the suppression of information that is irrelevant for the pursuit of an internal goal. While theta oscillations appear to play a critical role in information selection, alpha oscillations appear to mediate suppression (Jensen and Mazaheri 2010). When irrelevant information is suppressed from further processing, alpha oscillations emerge in the region that would process the information, e.g. alpha oscillations in visual cortex in the presence of visual distractors (Fries, Reynolds et al. 2001). When distractor stimuli are presented in a visual hemifield, the contralateral parietal-occipital cortex exhibits alpha oscillations that correlate with performance (Sauseng, Klimesch et al. 2009). When alpha-frequency TMS is delivered to the parietal-occipital cortex contralateral to distractors, alpha oscillation power is increased (Thut, Veniero et al. 2011) and task

CONFIDENTIAL

performance is improved (Sauseng, Klimesch et al. 2009). Alpha oscillations are recruited both during input-gating (Sauseng, Klimesch et al. 2009) when attentional cues are presented prior to stimulus presentation and also during output-gating, when attention is shifted between internal representations (Wallis, Stokes et al. 2015).

The neural mechanism for how regions in the brain communicate is via synchronized electrical oscillations (Fries 2015). Therefore, alpha and theta oscillations within the context of output-gating are proposed to serve the critical role of providing functional connections between brain areas. Previous studies have found that connectivity between frontal and parietal regions is critical for cognitive control (Vincent, Kahn et al. 2008, Cooper, Wong et al. 2015, Antzoulatos and Miller 2016). Previous experiments have investigated the causal role of functional connectivity by synchronizing multiple brain regions and putting brain regions out-of-synch using non-invasive brain stimulation (Polania, Nitsche et al. 2012, Alagapan, Riddle et al. 2019, Reinhart and Nguyen 2019). However, there has not been an experiment that has investigated frequency-specific functional connectivity using two different functional bands: theta and alpha.

In this protocol, we investigate the causal role of functional interactions between frontal-theta dependent selection processes and posterior-alpha dependent suppression processes in the context of cognitive control by targeting theta and alpha oscillations in frontal and parietal cortex separately in phase one of the experiment. Theta and alpha oscillations are hypothesized to play complementary roles such that theta oscillations are excitatory (related to active processing) whereas alpha oscillations are inhibitory (related to suppression of processing). Thus, we hypothesize that rhythmic brain stimulation can be used to drive activity in opposite directions as demonstrated in the previous experiment upon which this experiment is built upon (Riddle, Scimeca et al. 2020). In the second phase of the experiment, we target functional connectivity between these regions. In particular, theta oscillations are hypothesized to play a critical role in orchestrating the prioritization and suppression of information across the cerebral cortex. Thus, we hypothesize that in-phase theta frequency connectivity will be causally related to working memory success, but alpha frequency connectivity will be inconsequential and anti-phase theta connectivity will be detrimental. Together these findings suggest an overall model by which the amplitude of theta oscillations in prefrontal and the amplitude of alpha oscillations in parietal play a causal role in prioritization and suppression respectively, but functional connectivity between frontal and parietal cortex within the theta frequency band alone is critical to these cognitive processes.

## 2.2 DOSE RATIONALE

Transcranial magnetic stimulation (TMS) is a safe, non-invasive, widely-used tool that applies focal electric fields to the brain using magnetic coils placed on the scalp (Rossi et al. 2009). On the first stimulation session of the study, participants will receive a motor thresholding procedure in which electrodes are attached to the first dorsal interosseous muscle of the right hand, or another muscle on the hand or arm that is accessible to be targeted by TMS to the motor cortex. The contralateral motor cortex will be targeted by single pulses of TMS with increased stimulator output until a motor evoked potential (MEP) is generated: defined as a near-instantaneous increase muscle activity greater than 200 microvolts. Next, the intensity of single pulse TMS will be lowered until a MEP is generated on five out of ten pulses. This is defined as the participant's motor threshold (Rossi et al. 2009). If the motor threshold cannot be determined via MEP, the experimenter will use visible twitches as a proxy for MEP. Participants will receive TMS at 120% of their motor threshold. Each train consists of 5 pulses of TMS. Trains are delivered at individualized theta frequency, individualized alpha frequency, or one of two arrhythmic control conditions that matches for the duration of individual alpha frequency (IAF) and individual theta frequency (ITF) with randomized inter-pulse intervals. Thus, "arrhythmic-theta" refers to five TMS pulses with a random inter-pulse interval that lasts the same duration of the theta train of pulses, and "arrhythmic-alpha" refers to five TMS pulses

CONFIDENTIAL

with a random inter-pulse interval that lasts the same duration as the alpha train of pulses. The duration of the trains is matched to control for non-frequency-specific effects of TMS. The minimum inter-pulse interval will be 20 milliseconds. Between every train will be at least 5 seconds. An inter-train-interval of 5 seconds or greater allows for any residual effects of stimulation to return to baseline. This intensity, inter-pulse-interval, and inter-train-interval is well within the safety guidelines set forth for repetitive TMS (Wassermann, 1998; Rossi et al., 2009) and has been used in similar paradigms as the one described here (Thut et al. 2011; Hanslmayr et al. 2014; Albouy et al. 2017). For phase one, participants receive trains to either frontal or parietal cortex for each stimulation session (session 4 and 5). For each session of phase one, participants receive trains in theta, alpha, arrhythmic-theta, and arrhythmic-alpha. For phase two, participants receive trains to both frontal and parietal cortex in both sessions (session 4 and session 5) using two TMS coils. In session 4 and session 5, participants will receive stimulation in either theta or alpha frequency. For each of sessions 4 and 5 of phase two, participants receive trains in-synchrony (five pulses delivered to both sites at the same time), anti-synchrony (five pulses delivered to each site with a 180-degree phase difference), arrhythmic-in-synchrony (five pulses delivered to both sites at the same time), and arrhythmic-independent (five pulses delivered to both sites randomly without any temporal relation). Theta frequency functional connectivity is hypothesized to play a causal role in the prioritization and suppression of working memory representations. Alpha frequency stimulation is included as a control to test for the frequency specificity of functional connectivity.

EEG will be collected using the Geodesic 400 system (EGI INC., Eugene, OR, USA). Collecting simultaneous EEG and TMS does not pose any additional risk over TMS on its own. EEG does not involve brain stimulation and is used purely for neuroimaging (minimal risk).

### 2.3 STUDY AIMS/HYPOTHESES

This study will provide a comprehensive investigation of the causal role and functional interactions between theta and alpha oscillations in the selection and suppression of information processing in the human brain. This will allow us to assess whether these oscillations support dependent cognitive processes, and if this dependence is fundamental in coordinating information processing in the brain.

We hypothesize that theta oscillations in frontal cortex play a causal role in the prioritization of working memory representations and alpha oscillations in parietal cortex play a causal role in the suppression of working memory representations. Furthermore, in-phase theta oscillations, but not alpha oscillations, are critical for synchronizing activity between frontal and parietal cortex. To investigate this model, we propose two phases to the experiment and aims that are defined as either a “primary outcome” or “secondary outcome.” Note that for each of these aims has a corresponding statistical analysis described in section 11.

*Phase One* overarching goal: Investigate the causal role of frontal theta and parietal alpha oscillations in the prioritization and suppression of working memory representations.

Aim 1 (primary outcome): Stimulation that is aligned to the endogenous activity of the brain (frontal theta and parietal alpha) is hypothesized to improve performance whereas the mismatched frequency of stimulation is hypothesized to decrease performance (frontal alpha and parietal theta). Performance is assessed using Pashler’s working memory capacity metric.

Aim 2 (primary outcome): Stimulation is hypothesized to increase the targeted frequency of stimulation relative to arrhythmic stimulation. This aim will provide evidence of target engagement, i.e. that stimulation is effective at modulating the targeted rhythm.

Aim 3 (secondary outcome): Theta and alpha oscillations are hypothesized to play antagonistic roles

CONFIDENTIAL

whereby theta oscillations are associated with an increase in neural excitability and alpha oscillations are associated with a decrease in neural excitability. Therefore, we will investigate the impact of stimulation on other frequency band. Theta stimulation is hypothesized to decrease the amplitude of alpha oscillations and alpha stimulation is hypothesized to decrease theta oscillations.

Aim 4 (secondary outcome): Theta oscillations in frontal cortex are hypothesized to play a causal role in precision of working memory representations. During the probe, the participant responds with a specific color from a comprehensive color wheel. Plus or minus 15 degrees around the color wheel is considered "correct." For the correct trials, the precision is calculated as the distance in degrees from the response of the participant to the actual color of the memory item. To investigate if theta oscillations play a causal role in precision, the impact of theta stimulation on precision relative to arrhythmic and as a function of visual field will be investigated.

Aim 5 (secondary outcome): Stimulation that is aligned to the endogenous activity of the brain is hypothesized to entrain neural activity. Inter-trial phase coherence (ITPC) quantifies alignment of neural oscillations across trials. Stimulation in frontal-theta and parietal-alpha is proposed to increase ITPC in a frequency specific manner relative to control stimulation.

*Phase Two Overarching Goal:* Investigate the causal role of in-phase theta-frequency between frontal and parietal cortex in the prioritization and suppression of working memory representations.

Aim 6 (primary outcome): Stimulation that is delivered in-phase to frontal and parietal cortex in the theta frequency is hypothesized to increased working memory capacity relative to anti-phase theta stimulation. Working memory capacity is quantified using Pashler's metric.

Aim 7 (primary outcome): Stimulation that is delivered in-phase to frontal and parietal cortex in theta frequency is hypothesized to increase functional connectivity between the regions in a frequency specific manner. Functional connectivity will be measured using weighted phase lag index. In addition, we hypothesize that in-phase theta frequency stimulation will increase WPLI magnitude for retro-cues to the right visual field greater than the increase for stimulation with a retro-cue to the left visual field. This hypothesis is motivated by the finding that the left hemisphere processes information for the contralateral visual hemifield and that theta oscillations are linked to the active processing of information.

Aim 8 (secondary outcome): Stimulation that is delivered in-phase is hypothesized to decrease the relative phase difference (phase lag) between the frontal and parietal cortex, whereas anti-phase stimulation is hypothesized to increase the phase lag. If stimulation entrained neural activity directly to the stimulation train, then this pattern of phase lag differences would be expected.

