**Aim 7 (primary outcome):** Stimulation that is delivered in-phase to frontal and parietal cortex in theta frequency is hypothesized to increase functional connectivity between the regions in a frequency specific manner. Functional connectivity will be measured using weighted phase lag index (WPLI). To calculate WPLI, first Morlet wavelet convolution is performed to extract instantaneous phase and amplitude for the frequency of interest for the two target sites. Next, the cross-spectral density is calculated (one signal multiplied by the complex conjugate of the other). From the cross-spectral density the imaginary component of the resulting signal is extracted. Then those imaginary values are averaged over the time frame of instance (here, the second half of the stimulation train). Finally, the magnitude of the resulting vector is taken to be the WPLI. This metric quantifies the consistency of phase lag between the two target regions and is weighted towards signals with a 90 or 270 degree offset to address a common confound in EEG, volume conduction. We hypothesize that in-phase theta-frequency stimulation will increase theta-frequency WPLI strength between frontal and parietal cortex. In addition, we hypothesize that in-phase theta frequency stimulation will increase WPLI magnitude for retro-cues to the right visual field greater than the increase for stimulation with a retro-cue to the left visual field. This hypothesis is motivated by the finding that the left hemisphere processes information for the contralateral visual hemifield and that theta oscillations are linked to the active processing of information. Using a two-way ANOVA with factors for TMS frequency (theta or alpha) and retro-cue direction (left or right), we hypothesize a significant interaction ( $p < 0.05$ ) between TMS frequency and retro-cue direction such that WPLI magnitude is the greatest for theta-frequency stimulation with a retro-cue to the right visual field. Post-hoc t-tests will be performed using Tukey's method to control for multiple comparisons. *Sensitivity analysis:* The frequency, topographic, and spatial specificity of these effects will be explored. Similar to Aim 2, the time-course of WPLI can be estimated using a sliding window to demonstrate if functional connectivity rises and peaks at the end of the stimulation train. Furthermore, the topographic increase in functional connectivity will be quantified across the scalp to see if the effect is specific to the targeted regions. Finally, the frequency specificity will be explored by calculating functional connectivity across the full spectral range (2-30 Hz) and the specificity of connectivity changes in frequency domain will be displayed. Together, these analyses will establish the robustness

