
of our a priori effect. Furthermore, these confirmatory sensitivity analyses avoid the multiple comparisons problem by relying on the initially established analyses.

**Aim 8 (secondary outcome):** Stimulation that is delivered in-phase is hypothesized to decrease the relative phase difference (phase lag) between the frontal and parietal cortex, whereas anti-phase stimulation is hypothesized to increase the phase lag. If stimulation entrained neural activity directly to the stimulation train, then this pattern of phase lag differences would be expected (because in-phase stimulation is delivered with zero phase lag and anti-phase stimulation is delivered with a phase lag). To calculate phase lag, first Morlet wavelet convolution is performed to extract instantaneous phase and amplitude for the frequency of interest for the two target sites. Next, the cross-spectral density is calculated (one signal multiplied by the complex conjugate of the other). From the cross-spectral density the phase angle is extracted, this is the phase lag. Then those phase lag values are averaged over the time frame of instance (here, the second half of the stimulation train). Finally, the angle of the resulting vector is taken to be the average phase lag. This metric quantifies the degrees of phase lag between the two target regions. Using a two-way ANOVA with factors for TMS frequency (theta or alpha) and TMS alignment (in-phase or anti-phase), we hypothesize a significant main effect ( $p < 0.05$ ) of TMS alignment such that phase lag is different between in-phase and anti-phase where in-phase decreases the phase lag and anti-phase increases the phase lag. We also hypothesize that this effect will be strongest for theta-frequency stimulation, which is hypothesized to be revealed as a significant main effect between TMS frequency and TMS alignment. Post-hoc t-tests will be performed using Tukey's method to control for multiple comparisons. *Sensitivity analysis:* Similar to Aim 7, the spread of stimulation effects in time, space, and frequency will be explored.

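### Aim 8 takes the full cross-spectrum angle with no stated protection against volume conduction, so a true anti-phase lag can be read as zero lag

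*Combined protocol and SAP*

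**What the plan says.** Section 2.3 states the Aim 8 hypothesis: "Stimulation that is delivered in-phase is hypothesized to decrease the relative phase difference (phase lag) between the frontal and parietal cortex", and anti-phase stimulation is expected to increase it. Section 11.1 gives the reason: "in-phase stimulation is delivered with zero phase lag and anti-phase stimulation is delivered with a phase lag". Section 2.2 gives the size of the delivered offset: "anti-synchrony (five pulses delivered to each site with a 180-degree phase difference".

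For the estimator, Section 11.1 (Aim 8) applies a wavelet transform at the two target sites, multiplies one signal by the conjugate of the other, and continues: "From the cross-spectral density the phase angle is extracted, this is the phase lag". The values are averaged over the second half of the train, and "Finally, the angle of the resulting vector is taken to be the average phase lag". The test is a main effect of TMS alignment. The sensitivity work covers spread in time, space and frequency.

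Aim 7, in the same section, starts from a cross-spectrum built in the same way at the two target sites, over the same part of the train, but then: "From the cross-spectral density the imaginary component of the resulting signal is extracted". The stated reason is that the index is "weighted towards signals with a 90 or 270 degree offset to address a common confound in EEG, volume conduction".

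All phase-two analyses are run on differences: in-phase minus arrhythmic-in-synchrony, and anti-phase minus arrhythmic-independent.

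**The concern.** Field spread carries one source to both recording sites with no delay, so it adds a zero-lag (real) term to the cross-spectrum. Aim 7 removes that term. Aim 8 keeps it, and its text names no spatial filter, source-level signal, reference rule or leakage check. MRI localisation is described for placing the coil, not for the EEG phase analysis.

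The term matters more here than in most phase analyses, because the two predicted outcomes are 0 and 180 degrees. With same-polarity spread the added term points at 0, so it works directly against the anti-phase prediction. Aim 8 is the plan's check on whether the two regions follow the phase relation that was delivered, and a null result could come from the measure and not from the brain.

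**Working it through.** The documents give no expected lag, spread or power for Aim 8, so there is no figure of the plan's to reproduce. The check asks how much leakage the planned estimator tolerates.

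**Inputs**
- Delivered lags of 0 and 180 degrees: Sections 2.2 and 11.1.
- 150 trials per phase-two condition: Section 4.1.
- Source coherence r and leakage v (fraction of amplitude reaching the other site): not in the documents, so assumed. The range is r = 0.2 to 0.7 and v = 0 to 0.3.

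**Model.** Two unit-power sources z1 and z2 have cross-spectrum S = r·exp(iφ). The recorded signals are a = z1 + v·z2 and b = z2 + v·z1, with same-polarity spread. Then

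E[a·conj(b)] = S + 2v + v²·conj(S).

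**Angle read by the Aim 8 estimator, in expectation**
- In-phase (φ = 0): r(1+v²) + 2v is positive, so it reads 0 at any leakage.
- Uncoupled (r = 0): 2v is positive, so it reads 0. Without leakage the angle is random.
- Intermediate, for example φ = 90: the angle is arctan[r(1−v²)/(2v)]. At v = 0.2 this is arctan(0.288/0.4) = 36 degrees for r = 0.3, and arctan(0.480/0.4) = 50 degrees for r = 0.5.
- Anti-phase (φ = 180): −r(1+v²) + 2v. It stays negative, and so reads 180, until v exceeds (1 − √(1−r²))/r. Then it flips to 0.

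| Assumed r | Leakage at which 180 flips to 0 |
|---|---|
| 0.2 | (1 − √0.96)/0.2 = 0.101 |
| 0.3 | (1 − √0.91)/0.3 = 0.154 |
| 0.5 | (1 − √0.75)/0.5 = 0.268 |
| 0.7 | (1 − √0.51)/0.7 = 0.408 |

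**With sampling error.** Mean absolute angle in degrees over 3,000 simulated runs of 150 values (figures vary by a degree or two between runs):

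| r | v | Anti-phase | In-phase | Uncoupled control |
|---|---|---|---|---|
| 0.3 | 0 | 172 | 8 | 89 |
| 0.3 | 0.2 | 31 | 3.5 | 6 |
| 0.3 | 0.3 | 8.5 | 2.6 | 4 |
| 0.5 | 0.2 | 160 | 2.5 | 6 |
| 0.7 | 0.2 | 174 | 1.6 | 6 |

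At r = 0.3 the separation between in-phase and anti-phase falls from about 163 degrees (no leakage) to 28 (20%) and 6 (30%). At r = 0.5 and 20% leakage it is still about 157.

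**Does the arrhythmic subtraction help?** An angle is not linear in the cross-spectrum, so subtracting angles does not remove the added 2v. At r = 0.3 and 30% leakage, anti-phase reads 8.5 degrees and its uncoupled control 4, a difference of about 4.5.

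**Could Aim 7's approach be used instead?** No. The imaginary part is proportional to sin φ, which is zero at both 0 and 180 degrees.

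**The case against.** Four points on the other side have force.

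**Aim 8 does not contradict Aim 7.** A reader might infer that the plan breaks its own rule by keeping what Aim 7 discards. It does not: only the real part separates 0 from 180 degrees, so Aim 8 must keep it. What is missing is protection of that part.

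**The direction is not uniform.** It is tempting to say that every condition is pulled toward 0. In-phase is already there, exact 180 holds until the flip, and opposite-polarity spread pulls toward 180.

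**The size rests on assumed values.** At coherence 0.5 to 0.7 and 20% leakage, anti-phase still reads 160 to 174 degrees. Nothing in the documents shows which regime applies. They speak of target sites and do not describe preprocessing for this outcome, so analysis of raw scalp signals is itself inferred from silence.

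**A false positive does not follow.** One might fear that field spread could pass for the predicted zero-lag pattern. The test compares in-phase with anti-phase, and spread common to both shrinks that difference; it does not create one. Nor can the limited room for in-phase to lower the lag be put down to field spread alone: its control delivers simultaneous pulses to both sites and may sit near zero lag by design.

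What remains is that the text, followed as written, permits an analysis in which a real anti-phase effect disappears.

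**Conclusion.** The concern stands as a gap in the Aim 8 specification. With same-polarity spread, the planned angle biases intermediate lags toward 0 and turns a true 180-degree lag into 0 above a leakage threshold of 10% to 41% of amplitude, for source coherence of 0.2 to 0.7. Weak entrainment makes it vulnerable; strong entrainment largely does not. The planned subtraction of arrhythmic angles does not repair it.

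The conclusion rests on a symmetric two-source model with equal power, and on assumed leakage and coherence. It shows what can happen, not that it will happen in this trial. The consequence is a lost contrast on a secondary outcome, which Section 11.1 would report as inconclusive. The primary outcomes are not affected. The change is worth making before the phase-two EEG is analysed.

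**What to change.** Amend the Aim 8 text in Section 11.1 to:

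1. Compute phase on spatially filtered signals (surface Laplacian or current source density) or on leakage-reduced source signals at the two targets.
2. Fix the reference and a polarity rule in advance, since a sign reversal at one site is exactly a 180-degree shift.
3. Report the unfiltered scalp result as a sensitivity analysis.

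Subtracting complex cross-spectra before taking the angle is not a safe primary measure for the in-phase condition, because arrhythmic-in-synchrony may carry genuine zero-lag coupling that would be removed too. In simulation at 20% leakage, with in-phase coherence 0.3, the in-phase difference angle is random (mean absolute value about 90 degrees) when the control is equally coupled, and about 158 degrees when the control's coherence is 0.5. For anti-phase minus arrhythmic-independent, complex subtraction returned 160 to 174 degrees at 10% to 30% leakage and coherence 0.2 to 0.5, so it may serve there as a sensitivity check.

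The cost is one processing step on EEG already planned, plus a short specification; no new data are needed. The downside is that a Laplacian weakens broad or deep sources.
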